## **7.5 Notes on specific trial visits**

### **7.5.1 Screening**

Patients will be recruited via two methods:

- Elective surgery theatre lists
- Trauma surgery theatre lists

In the event of trauma and elective surgery, patients will be contacted prior to their surgery by a member of the research team and invited to participate.

In the event of presentation in an outpatient setting, patient referrals from their general practitioner or emergency department will be reviewed and patients will be contacted via phone or email to participate in the study.

Patients who are undergoing surgery or have sustained an injury at or distal to the distal one third of the tibia will be eligible.

Patients will be consented and enrolled in the trial prior to surgery and randomisation and commencement of treatment will occur immediately afterwards. In an outpatient setting, if patients have presented within 72 hours of injury, eligibility criteria will be assessed and patients will be consented, enrolled, randomised and treatment commenced during that outpatient visit. If patients are unable to commence their treatment within 72 hours of injury they will not be deemed eligible to participate.

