### 4.3 Trial population

Patients aged 18 and over will be eligible for the trial. Patients undergoing elective or emergency foot and ankle surgery and the five sites will be invited to participate.

Patients who are unable to provide informed consent to participate in the trial will be excluded.

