### 4.4 Eligibility criteria

Participants will be assigned to a randomised trial treatment only if they meet all of the inclusion criteria and none of the exclusion criteria.

---

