#### 4.4.1 Inclusion criteria

Each patient needs to meet the following criteria to be eligible to participate in the trial:

- Patients need to be aged 18 and over to participate in the trial. This is because most fractures in the lower limb in children are treated non-operatively. In addition, most sites have limited numbers of younger patients who have surgery for foot or ankle problems, recruitment of people under the age of 18 is unfeasible.
- Patients need to be able to provide informed consent for the trial via a signed and dated consent form. Patients who are unable to provide informed consent because of (for example) cognitive impairment will be excluded.
- Patients who present to Peninsula Health, Frankston Private Hospital, Holmesglen Private Hospital, Beleura Private Hospital or Cabrini Brighton Private Hospital for surgery of the foot and ankle, either elective or emergency, will be eligible to participate.

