#### 4.4.2 Exclusion criteria

Patients meeting the following criteria will be excluded from the trial:

- Current or recent (ie less than three months prior to randomization) use of vitamin C, either as an isolated substance or as part of a multi-vitamin tablet. This is because the vitamin C dosing will not be standardized if patients are also taking the vitamin, and there is potential for overdosing. Vitamin C has a half-life of 10-20 days and therefore a long exclusion period is required.
- Patients who are pregnant or breastfeeding will be excluded due to the unknown safety risks in this patient population.
- Patients who are unable to commence taking the placebo/vitamin C medication within 72 hours after their surgery will be excluded from the trial
- Patients unable or unwilling to take oral medications.
- Patients who are vegan (as the placebo acidophilus is dairy based)

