#### **4.7 Recruitment and identification of potential participants**

Patients will be recruited in the following ways:

- Following HREC approval, elective and trauma theatre lists will be screened and potential patients with elective and trauma foot and ankle surgery will be identified and asked to participate in the trial. They will then be contacted by a member of the research team.
- A poster advertising the trial will be available in fracture clinic and elective orthopaedic clinic and patients will have an opportunity to discuss participating in the trial directly with their treating clinician who will then pass on the details to a member of the research team.
- Clinicians in the fracture and elective clinics will invite eligible patients to participate in the trial.

Contact details for the patients, including an email address and mobile phone number, will be passed on to a member of the research team for contact as well as access to the electronic medical record for patient contact information.

The target trial population is all patients aged 18 and over who present for elective or trauma surgery of the foot and ankle. For this feasibility study, it is estimated that approximately 100 patients will need to be enrolled to assess the feasibility of the trial.

The recruitment period will be six months.

Recruitment will be done at the following sites:

- Peninsula Health – Frankston Hospital
- South East Orthopaedic Surgery – Frankston Private Hospital, Beleura Private Hospital, Holmesglen Private Hospital, Cabrini Brighton Private Hospital

Recruitment will most commonly occur in the outpatient setting. For patients presenting with trauma-related conditions, recruitment may occur in the inpatient setting.

Prior to performing any trial-specific intervention, a signed consent form will be obtained for each participant. The process will be that the investigator or delegated member of the trial team will discuss the trial with the potential participant. The investigator will provide the Participant Information and Consent Form to the patient. This document will describe the purpose of the trial, the procedures to be followed, and the risks and benefits of participation.

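### Section 7.5.1 makes injury alone sufficient for entry and runs the 72 hours from injury, against the surgical eligibility criteria in Sections 4.3 to 4.4.2

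*Protocol*

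**What the plan says.** The formal criteria describe a surgical population. Section 4.3: "Patients undergoing elective or emergency foot and ankle surgery and the five sites will be invited to participate". Section 4.4.1 requires that the patient presents to one of the sites "for surgery of the foot and ankle, either elective or emergency, will be eligible to participate". Section 4.4.2 adds a time limit counted from the operation: "Patients who are unable to commence taking the placebo/vitamin C medication within 72 hours after their surgery will be excluded from the trial". Section 4.4 makes the lists binding: "Participants will be assigned to a randomised trial treatment only if they meet all of the inclusion criteria and none of the exclusion criteria".

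Section 7.5.1 (Screening) says something different. On population: "Patients who are undergoing surgery or have sustained an injury at or distal to the distal one third of the tibia will be eligible". For outpatients who present within 72 hours of injury, once eligibility has been assessed, "patients will be consented, enrolled, randomised and treatment commenced during that outpatient visit". The limit it then sets runs from injury: "If patients are unable to commence their treatment within 72 hours of injury they will not be deemed eligible to participate". For patients found before surgery, the same section has consent first, with randomisation and treatment straight after the operation.

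Section 7.4 is mixed. It gives the 72-hour limit as running from injury or surgery, but it defines a potential participant by a procedure. It has patients seen in an outpatient clinic contacted within 72 hours after their operation. It also states that for someone injured and then operated on, the clock starts once surgery is over.

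**The concern.** Two instructions to sites disagree on who may be randomised and when the first capsule is taken. This is not a detail that an analysis plan could settle, because it decides who is in the trial.

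Recruitment capability is one of the primary feasibility outcomes in Section 3.2, and the larger trial would be planned on it. If one site applies Section 4.4.1 and another applies Section 7.5.1, the recruitment result does not describe a single eligible pool. The incidence estimate in Section 11.3 is defined at six months after surgery, and Section 7.5.2 times the final visit from surgery. A participant who never has an operation has neither.

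A wrong enrolment cannot be undone. The Replacements section (numbered 5.2.4 in the body, 7.5.4 in the contents) forbids replacing anyone randomised, and Section 11.2 keeps all randomised participants in the analysis.

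**Working it through.** There is no planned figure to reproduce. The check is a comparison of the statements, followed by what the outpatient route leads to.

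**Step 1. The statements side by side.**

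| Place in Protocol | Who is eligible | Start of the 72 hours |
|---|---|---|
| Section 4.3 | Surgical patients | Not stated |
| Section 4.4.1 | Presents for foot and ankle surgery | Not stated |
| Section 4.4.2 | Not stated | Surgery |
| Section 7.4 | Defined by a procedure | Injury or surgery; after surgery if an injury is later operated on |
| Section 7.5.1, theatre-list route | Surgical patients | Treatment begins straight after surgery |
| Section 7.5.1, outpatient route | Surgery or injury | Injury |

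Only the outpatient route in Section 7.5.1 makes injury alone sufficient and uses an injury-only clock.

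**Step 2. Follow that route for a patient seen within 72 hours of injury.** Suppose the patient is randomised and takes the first capsule at the visit.

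- If no operation follows, Sections 4.3 and 4.4.1 are not met. The surgery-based exclusion in Section 4.4.2 cannot be applied. The final visit (Section 7.5.2) and the incidence time point (Section 11.3) have no origin.
- If an operation follows, the 50-day course began before it. Section 7.4 would have started the clock only afterwards.
- If the operation had already taken place, the patient is surgical, but the limit that applies under Sections 4.4.2 and 7.4 is the one from surgery, not from injury.

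None of the three cases agrees with the formal criteria.

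**Step 3. Can the scripted data catch it?** The screening questions in Section 7.4 ask for the date and time of surgery. The baseline list there records the date of surgery. Neither asks when the injury occurred, so the injury clock in Section 7.5.1 has no scripted check.

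**Step 4. Size.** The Protocol does not say how many outpatients would be fresh injuries, so the number affected cannot be computed. Against the target of about 100 in Section 4.7, each such participant is 1/100, or 1 percentage point.

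For the second case in Step 2, the shift in dosing can only be illustrated. Let the first capsule be on day s after injury (s = 0 to 3) and surgery on day d. The delay d is an assumption; the Protocol gives none. Capsules taken before surgery = d − s. The last of 50 daily capsules falls on post-operative day s + 49 − d.

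| Assumed d | Capsules before surgery | Share of 50 | Last capsule, post-operative day |
|---|---|---|---|
| 4 | 1 to 4 | 2 to 8% | 45 to 48 |
| 7 | 4 to 7 | 8 to 14% | 42 to 45 |
| 14 | 11 to 14 | 22 to 28% | 35 to 38 |

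Under the surgery clock, with a start on post-operative day 0 to 3, the last capsule falls on day 49 to 52.

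**The case against.** The best defence is that Section 7.5.1 does not stand alone. Its outpatient sentence has eligibility assessed before consent, Section 4.4 requires every criterion to be met, and Section 7.4 asks each patient when surgery took place. A site that applied all of this would turn away a patient with no operation. That is a fair reading and may limit how many are wrongly enrolled. It does not remove the conflict. Section 7.5.1 states outright that injury suffices, and even for a patient awaiting surgery it starts capsules at the visit, before the operation.

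Three stronger readings are tempting, and the Protocol does not support them.

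- A reader might infer that non-operated injuries are meant to be included. The synopsis population and its reference to the index surgery, Sections 4.3, 4.4.1, 4.4.2 and 4.7, the schedule of assessments, the procedure-based definition in Section 7.4, and Sections 7.5.2 and 11.3 all point to surgery. The injury wording looks stray.
- A reader might infer from "Recruitment will most commonly occur in the outpatient setting" (Section 4.7) that most participants are affected. That sentence does not say how many outpatients are fresh injuries, and the next one notes that trauma patients may be recruited as inpatients.
- A reader might infer that the last review is timed from injury, because the synopsis says so at that one point. The same synopsis row counts enrolment from the index surgery and calls all four reviews post-operative, so this is loose wording and not a second follow-up schedule.

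**Conclusion.** The contradiction is real and should be corrected, preferably before recruitment starts. Section 7.5.1 departs from the binding criteria on both population and start of treatment, and a site that follows it can randomise patients whom Sections 4.4.1 and 4.4.2 do not admit.

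The consequence is limited. It blurs the eligible pool behind the recruitment result and the denominator of the post-surgery incidence, by an amount that cannot be estimated and may be small. The dosing shifts above depend wholly on assumed delays and are not an estimate of what will happen. A reader might go on to infer that the comparison of vitamin C with placebo is biased; it is not, because allocation is random whichever route a patient enters by. Trauma patients recruited from theatre lists before surgery are handled consistently, if the injury limit in Section 7.5.1 is read as belonging to the outpatient route.

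**What to change.** Assuming the surgical population is intended:

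- In Section 7.5.1, delete the words that make a sustained injury sufficient, and delete the limit of 72 hours from injury. State that injured outpatients awaiting surgery may be consented in clinic but are randomised and start capsules within 72 hours after the index operation.
- In Section 7.4, give the 72-hour limit from surgery only.
- Time the visits from surgery in the synopsis (trial description and participant duration) and in Section 2.2, where they are now given as after injury or after injury/surgery.
- Record the date and time of the first capsule. The surgery date is already collected.

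Only if the sponsor does intend to include non-operated injuries should Sections 4.3, 4.4.1, 4.4.2, 7.5.2 and 11.3 be extended, with an injury-based clock, visit timing and incidence time point limited to those patients.

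The cost is a handful of text edits and one added field at an existing contact. The drawback is that, under a surgery-only clock, patients operated on late start vitamin C later after their injury.

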### **7.5.2 Final trial visit**

The final trial visit will occur six months following the patient's surgery. There are no special procedures or evaluations at this time except the standard questions. Trial results and randomisation results will be shared with participants via email at the conclusion of the trial. It is not expected patients will need to be contacted in the future.

Any adverse events as a result of the medication will be followed until resolution and appropriate referrals followed up.

### **7.5.3 Unscheduled visit**

Patients will be advised to contact a member of the research team should they have an unscheduled visit (for example, to the Emergency Department) with either an exacerbation of their condition or side effect of their medication. Patients will be asked at each review whether they had presented to another centre for their injury or side effect at any stage.

### **7.5.4 Telehealth consultations**

In light of the recent coronavirus pandemic and shift to telehealth consultations, the need for potential telehealth follow up has been made. It is expected that patients will be followed up by standard face-to-face appointments but, if required, follow up can be via videoconference using secure videoconference programs as recommended by the Department of Health – these are Health Direct (Peninsula Health) or CoviU (Frankston Private Hospital, Holmesglen Private Hospital, Cabrini Brighton Private Hospital and Beleura Private Hospital). These videoconferencing systems are secure and recommended by the federal Department of Health for telehealth consultations.

---

## 5.2 Treatment discontinuation, participant withdrawals and losses to follow up

### 5.2.1 Discontinuation of treatment - participant remains in trial for follow up

Participants who discontinue trial treatment will remain in the trial. The remaining trial procedures should be completed as indicated by the trial protocol.

Participants may discontinue trial treatment for the following reasons:

- Participant request to discontinue trial intervention
- Investigator decision to discontinue a participant from the trial intervention if the participant:
  - Demonstrates significant non-adherence with the trial intervention
  - Experiences a serious or intolerable adverse event such that continued trial intervention would not be in the best interest of the participant
  - Develops, during the course of the trial, symptoms or conditions listed in the exclusion criteria
  - Requires a medication that is prohibited by the protocol
  - Requires early discontinuation for any other reason

The investigator may also withdraw all trial participants from the trial treatment if the trial is terminated.

The procedure for transitioning a participant off the trial drug and/or onto alternate therapy is as follows – immediate cessation of the intervention medication and opening of randomization envelope so treating clinicians are aware of the dosage.

For the safety of all participants ceasing trial treatment, the protocol-specified safety evaluations should be undertaken to capture new safety events and to assess existing, unresolved safety events. All scheduled follow-ups of trial participants should also occur following treatment discontinuation, where possible.

In addition to the safety evaluations, the data to be collected at the time of trial intervention discontinuation will include the following:

- Reason for discontinuation
- Assessment for CRPS

A dedicated Case Report Form (CRF) page will capture the date and the specific underlying reason for discontinuation of the trial intervention.

The participant should remain in the trial for scheduled visits for trial assessments (follow-up) per protocol.

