Valid outcome measures of CRPS have been described(13)(14). Similar to the protocol described by Zollinger(2), patients will undergo a clinical assessment two weeks post injury, six weeks post injury, twelve weeks post injury and twenty-six weeks post-injury. This

---

correlates to standard routine practice, where patients are assessed at two weeks post-operatively for a wound check, six weeks post-operatively for clinical review and also commonly twelve and twenty-six weeks post-operatively for ongoing assessment of response to surgery.

Patients will be assessed by their treating clinician according to the Budapest Criteria(1):

- A: continuing pain, which is disproportional to any inciting event
- B: The patient must report at least one symptom in three of the four following categories:
  - Sensory- reports of hyperaesthesia and/or allodynia
  - Vasomotor – reports of temperature asymmetry and/or skin colour changes and/or skin colour asymmetry
  - Sudomotor/oedema – reports of oedema and/or sweating changes and/or sweating asymmetry
  - Motor/trophic – reports of decreased range of motion and/or motor dysfunction (weakness/tremor/dystonia) and/or trophic changes (hair/nail/skin)
- C: The clinician must observe at least one sig at the time of the evaluation in two or more of the following categories:
  - Sensory- evidence of hyperalgesia (to pinprick) and/or allodynia and/or deep somatic pressure and/or joint movement
  - Vasomotor – evidence of temperature asymmetry and/or skin colour changes and/or skin colour asymmetry
  - Sudomotor/oedema – evidence of oedema and/or sweating changes and/or sweating asymmetry
  - Motor/trophic – evidence of decreased range of motion and/or motor dysfunction (weakness/tremor/dystonia) and/or trophic changes (hair/nail/skin)
- D: There is no other diagnosis that better explains the signs and symptoms

A randomised controlled trial to investigate the dose-response relationship between vitamin C and the prevention of complex regional pain syndrome in the lower limb has yet to be reported in the literature and can potentially revolutionise how we treat these patients. It is a relatively cheap, safe, potentially effective preventative in lower limb trauma that may help prevent the catastrophic consequences of complex regional pain syndrome in the lower limb.

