### 5.2.9 Discontinuation from trial intervention

Participants who discontinue trial treatment will remain in the trial. The remaining trial procedures should be completed as indicated by the trial protocol.

Participants may discontinue trial treatment for the following reasons:

- Participant / legal guardian request to discontinue trial intervention
- Investigator decision to discontinue a participant from the trial intervention if the participant:
  - Is pregnant
  - Experiences a serious or intolerable adverse event such that continued trial intervention would not be in the best interest of the participant
  - Develops, during the course of the trial, symptoms or conditions listed in the exclusion criteria
  - Requires a medication that is prohibited by the protocol
  - Requires early discontinuation for any other reason

The investigator may also withdraw all trial participants from the trial treatment if the trial is terminated.

The procedure for transitioning a participant off the trial drug and/or onto alternate therapy is as follows: patients will be advised to cease taking the medication immediately and return the unused medication to the researcher.

For the safety of all participants ceasing trial treatment, the protocol-specified safety evaluations should be undertaken to capture new safety events and to assess existing, unresolved safety events. All scheduled follow-ups of trial participants should also occur following treatment discontinuation, where possible.

In addition to the safety evaluations, the data to be collected at the time of trial intervention discontinuation will include the following:

- Reason for discontinuing medication
- Any adverse effects
- Involvement of other practitioners in treatment of adverse events

A dedicated Case Report Form (CRF) page will capture the date and the specific underlying reason for discontinuation of the trial intervention.

The participant should remain in the trial for scheduled visits for trial assessments (follow-up) per protocol.

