### 6.3 Breaking of the trial blind

#### 6.3.1 On trial

The randomisation code for an individual participant may only be unblinded in emergency situations, where the Investigator decides a participant cannot be adequately treated without knowing the identity of their treatment allocation. Specifically, if the patient reports symptoms of vitamin C toxicity such as severe gastrointestinal upset or kidney stones, the randomisation code will be broken in order to communicate to the patient's treating physician(s) the vitamin C dosing. To break the randomisation code the Investigator must open the emergency unblinding envelopes provided, or contact the randomisation

---

facility/personnel. If any unblinding envelope is opened, the time, date, participant number and reason for opening must be documented.

Blinding is imperative in this trial to avoid bias and answer the specific research question and all researchers are aware of the importance of this.

It is not expected that inadvertent unblinding will occur due to strict randomisation and blinding protocols.

[figure not shown]

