### 5.2.2 Withdrawal of consent - participant withdraws from all trial participation

Participants are free to withdraw from the trial at any time upon their request or the request of their legally acceptable representative. Withdrawing from the trial will not affect their access to standard treatment or their relationship with the hospital and affiliated health care professionals.

---

For the safety of all participants ceasing trial treatment, reasonable efforts should be made to undertake protocol-specified safety evaluations to capture new safety events and to assess existing, unresolved safety events following withdrawal.

If patients have severe symptoms they will be referred to the most appropriate treating clinician (for example, urology in the setting of kidney stones). Patients will be advised to cease treatment and randomization treatment arm will be made known to patient and clinician.

A dedicated Case Report Form (CRF) page will be used to capture the date of participant withdrawal of consent.

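### The procedure for stopping trial capsules opens the randomisation envelope for non-emergency stops, contradicting the protocol's emergency-only unblinding rule and allowing some later CRPS ratings to be made unblinded

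*Protocol*

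**What the plan says.** The numbers 5.2.1 and 5.2.2 each occur twice in the protocol. Here they mean the two later sections, on discontinuation of treatment and on withdrawal of consent.

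- **Section 5.2.1, Discontinuation of treatment.** The reasons for stopping include "Participant request to discontinue trial intervention", "Demonstrates significant non-adherence with the trial intervention" and "Requires early discontinuation for any other reason". One procedure follows for all of them: "immediate cessation of the intervention medication and opening of randomization envelope so treating clinicians are aware of the dosage". The participant then stays in the trial for scheduled visits. A CRPS assessment is also collected at discontinuation, with no statement of whether it comes before or after the envelope is opened.
- **Section 5.2.9, Discontinuation from trial intervention.** A near-identical list leads to a different procedure: "patients will be advised to cease taking the medication immediately and return the unused medication to the researcher". No envelope is mentioned.
- **Section 6.3.1, On trial.** The code "may only be unblinded in emergency situations", when adequate treatment depends on knowing the allocation. Severe gastrointestinal upset and kidney stones are the named examples.
- **Section 6.3.2, On completion of the trial.** Codes are withheld until every participant's data are entered and the database is final, emergencies excepted.
- **Section 4.1, Overall design.** Patients and clinicians stay blinded for the whole study.
- **Outcome rating.** Section 2.2 states: "Patients will be assessed by their treating clinician according to the Budapest Criteria". Section 7.4 allows either a research team member or the treating clinician.
- **Section 11.2.** All randomised participants are analysed by intention to treat.

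**The concern.** A site cannot follow both procedures for the same event. If it follows section 5.2.1, each non-emergency stop breaches section 6.3.1. If it follows section 5.2.9, it ignores section 5.2.1.

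The conflict reaches the outcome because the people told the dosage, the treating clinicians, are among those permitted to rate CRPS afterwards. The Budapest criteria rest partly on judgement: whether pain is disproportionate, whether signs are observed, and whether another diagnosis fits better. A positive finding at any one visit makes the event. The group affected is also selected after randomisation, by stopping treatment. If reasons for stopping differ between arms, loss of blinding would differ too. Section 6.3.1 itself calls blinding imperative.

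**Working it through.** The protocol has no figure of its own to reproduce here, so the check is mainly a comparison of texts.

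**Step 1: where the rules agree and where they conflict.**

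| Reason for stopping in 5.2.1 | 5.2.1 | 6.3.1 | Result |
|---|---|---|---|
| Serious or intolerable adverse event that meets the 6.3.1 test | Open envelope | Code may be broken | Agree |
| Adverse event that does not meet that test | Open envelope | Stay blinded | Conflict |
| Participant request | Open envelope | Stay blinded | Conflict |
| Significant non-adherence | Open envelope | Stay blinded | Conflict |
| Any other reason | Open envelope | Stay blinded | Conflict |

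Section 5.2.3 has participants with gastrointestinal upset stop capsules, without requiring it to be severe. Section 6.3.1 names severe upset. Milder upset therefore falls in the second row.

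**Step 2: are outcome visits left after the envelope is opened?** Capsules start within 72 hours (3 days) and run for 50 days, so they end by about day 3 + 50 = 53. The third review is at 10 weeks (day 70) at the earliest under section 3.2, and the fourth is at 26 weeks. Every early stop therefore precedes at least two scheduled CRPS assessments, provided the participant is still CRPS-free and attending.

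**Step 3: can the rater be unblinded?** Sections 2.2 and 7.4 permit the treating clinician to rate, and section 5.2.1 informs the treating clinician. The table in section 6.2 names outcome-assessing clinicians among those kept unaware (in its allocation-concealment column), but nothing bars a clinician who has learned the arm from rating later visits.

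**Step 4: scale, by assumption only.** The protocol gives about 100 participants (at least 50 per arm) and no discontinuation rate.

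- Opened envelopes = 100 × d. With d = 5%, this is 5. With d = 20%, it is 20.
- Expected CRPS events in the whole trial = 50 × pc × (1 + RR), where pc is the control risk and RR the risk ratio. Assume RR = 0.5. With pc = 5%: 50 × 0.05 × 1.5 = 3.75. With pc = 30%: 50 × 0.30 × 1.5 = 22.5. Only the 30% has an echo in the protocol (section 2.2, tibial shaft fractures).
- Expected events among those who stop, at the same average risk (0.75 × pc): from 5 × 0.0375 = 0.19 to 20 × 0.225 = 4.5. Events diagnosed before the stop would lower these figures.

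With few events in total, one or two altered ratings could move the estimate. These figures show scale only. The contradiction does not depend on them.

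**The case against.** Several points on the other side stand.

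- **The unblinded clinician is a possible rater, not a certain one.** Section 7.4 also lets a research team member examine the participant, and says that study researchers conduct the follow-up history and examination. A reader might infer that every participant who stops is then rated unblinded. The documents do not show that.
- **Some non-adherent participants may have no later ratings.** Section 5.2.6 withdraws participation after more than three missed doses in the preceding two weeks. That conflicts with continued follow-up under section 5.2.1, but it could reduce the number affected.
- **The withdrawal section is not the same fault.** Section 5.2.2 (Withdrawal of consent) states: "Patients will be advised to cease treatment and randomization treatment arm will be made known to patient and clinician". Read alone, this looks like a second routine unblinding. It stands in a paragraph on severe symptoms, with kidney stones as the example, so it largely agrees with section 6.3.1. It also concerns people leaving all trial participation, for whom no further CRPS rating is expected.
- **Allocation concealment is not shown to fail.** Allocation is blocked, investigators hold the envelopes, and investigators may recruit. A reader might infer that opened envelopes reveal later assignments. How much they would reveal depends on block size, which section 6 does not state.
- **The trial does not lose its double-blind status.** Individual, documented code breaks do not by themselves undo a double-blind design.
- **CRPS is a secondary outcome of a feasibility study.** No primary objective depends on a blinded CRPS rating. The protocol also expects good compliance (section 4.5) and very few adverse events (opening of the safety chapter).

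These points limit the consequence. None of them reconciles section 5.2.1 with sections 4.1, 5.2.9, 6.3.1 and 6.3.2.

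**Conclusion.** The contradiction is on the face of the text and needs no assumption. Section 5.2.1 makes opening the envelope part of any treatment discontinuation, while four other sections either restrict unblinding to emergencies, promise blinding throughout, or describe the same step without it. For adverse events that meet the emergency test the sections agree, so the conflict is confined to the other reasons for stopping.

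The consequence is that some later CRPS ratings, of participants who remain in the intention-to-treat comparison, could be made by someone who knows the arm. That may bias the secondary comparison. Neither its direction nor its size can be derived from the protocol, and the 5 to 20 opened envelopes rest on an assumed 5% to 20% discontinuation. The point still deserves correction in a feasibility study, because this protocol is being tested for a possible larger trial.

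**What to change.** Reconcile section 5.2.1 (Discontinuation of treatment) with sections 4.1, 5.2.9, 6.3.1 and 6.3.2, so that one unblinding rule applies and non-emergency discontinuation no longer conflicts with the stated blinding. Leave emergency access to the code intact. How treatment is stopped, and what care follows, is for the sponsor to settle.

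Add that, wherever a code is broken, the break is logged (section 6.3.1 already requires time, date, participant number and reason) and the remaining CRPS assessments are done by an existing team member who does not know the arm. The withdrawal-of-consent section needs only a cross-reference to section 6.3.1.

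The cost is a wording amendment and minor scheduling effort among the existing assessors.
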